2.7 ALLOWED WINDOW OF EACH SCHEDULE SEE 2.6

3. SELECTION AND WITHDRAWAL OF SUBJECTS

3.1 INCLUSION CRITERIA

In order to be eligible to participate in this study, a subject must meet all of the following criteria.

- Eligible for intramedullary nailing.
- Fracture type is classified as 3-partB or 4-part fracture in 3D-CT classification (Nakano), and combination with a subtype P in lateral classification (Ikuta) at preoperative CT assessment.
(In the case of classified in X-ray at preoperative: Classified as Type 4 or Type5 in Jensen classification, and combination of subtype P in lateral classification (Ikuta))
- Japanese Male or female
- > 20 years of age
- Primary closed intertrochanteric fracture of the femur
- Subjects willing to return for follow-up evaluations.

Study Specific Requirements for Investigator/Site

- Site can take X-ray or CT imaging, which classifies the fracture type appropriately at preoperative, also can take CT imaging at immediate postoperative and 3 weeks.

3.2 EXCLUSION CRITERIA

A potential subject who meets any of the following criteria will be excluded from participation in this study.

Absolute contraindications include:

- Patient who cannot take CT image within 3 days and 3 weeks after surgery.
- Uncooperative patient or patient with neurologic disorders who are incapable of following directions.
- Product contra indications:

-
- A medullary canal obliterated by a previous fracture or tumor.
 - Bone shaft having excessive bow or deformity
 - Lack of bone substance or bone quality which makes stable seating of the implant impossible.
 - All concomitant diseases that can impair the functioning and the success of the implant
 - Infection
 - Insufficient blood circulation
 - Skeletally immature patients

3.3 SUBJECT WITHDRAWAL

It is recognized that the subject's participation in this trial is entirely voluntary, and that she/he may refuse to participate and may withdraw from participation at any time without jeopardy to any future medical care. It is also recognized that the investigator, at his/her discretion, may withdraw a subject from this study based upon his/her professional judgment. In event of subject withdrawal, applicable local procedures should be followed.

If a patient is withdrawn or rescinds their consent, a "Lost to Follow-up" case report form should be completed detailing the reason for the patient withdrawal. The site should also notify their Ethical Committee (EC) if applicable. If a patient is withdrawn from the study by the investigator, the patient should be notified of their removal by a letter from the site or according to the local EC.

It is required that patients return within the defined follow-up period to complete all study assessment forms and radiographs. Patients that miss or will not return for follow-up are not considered "protocol deviations" or "lost to follow-up."

Specific criteria for withdrawal (if applicable)

If patients meet any of the following criteria, a subject withdrawal form should be completed, and below data documented on the form:

1. Patient rescinds consent in writing: Date of occurrence
2. Patient Death: Reason and date of death should be documented
3. Implant Removal: Date of revision, all component part numbers removed, and reason for revision

Replacement of individual subjects after withdrawal

Subjects will not be replaced, unless they do not have surgery or intraoperatively it has been recognized the patient is not eligible for a treatment with ZNN CM Asia.

Follow-up of subjects withdrawn from treatment

Subject withdrawn from the study will obtain standard medical treatment as foreseen at the investigational site.

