7.3 HANDLING OF MISSING AND INCOMPLETE DATA

Data will be considered “missing” for the primary endpoint if this outcome cannot be determined or is unavailable for a subject. Every effort will be made to collect the data necessary to evaluate the primary endpoint. Subjects who have been lost to follow-up and/or are missing CT data at 3 weeks will not be included in the primary study analysis.

Sensitivity analyses will be performed to assess the impact of missing data on the primary study analysis. These analyses may include a best-case and worst-case imputation as well as a tipping point analysis.

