7.4 DATA ANALYSES

Data will be analysed using SAS 9.0 or higher. The Type I error rate for the primary study analysis will be 0.05. Comparisons for secondary, exploratory, and safety analyses will be two-sided comparisons using $\alpha = 0.05$, with no adjustment for multiple comparisons.

Primary Analysis: The primary analysis will be performed on the set of patients with non-missing CT data at 3 weeks (Full Analysis Set (FAS)). Sensitivity analyses will be presented for the intention-to-treat (ITT) patient group. A two-tailed Pearson’s Chi-Square test at $\alpha = 0.05$ will be used to assess the study hypotheses and determine whether there is a statistically significant difference between investigational and control groups with regard to the maintenance rate of immediate post-operative reduction position.

Secondary Analysis: Analyses for secondary endpoints will be on the FAS, and will only use those cases with complete data for the endpoint being analysed.

Continuous data (e.g. age, BMI) will be reported using mean, standard deviation, median, and range. Comparisons between Investigational vs Control groups with regard to continuous baseline and secondary outcomes will be performed using standard statistical tests and will be chosen as appropriate for the scale and distribution of the measures being analyzed. For example, a t-test, Wilcoxon test, or one-way ANOVA (as appropriate) may be performed to assess differences in means/medians.

Categorical data (e.g. gender, classification of fracture) will be reported using frequency and percentage. Comparisons of Investigational vs Control with regard to categorical baseline, secondary and safety outcomes will be performed using standard statistical tests and will be chosen as appropriate for the scale and distribution of the measures being analyzed. For example, categorical outcomes may be compared for investigational and control groups using the Pearson’s chi-square test.

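### Section 3.3 lets an investigator who knows the arm withdraw a randomised patient on judgment alone, and Section 7.3 can then drop that patient from the primary analysis

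*Combined protocol and SAP*

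**What the plan says.** Section 3.3 states that "the investigator, at his/her discretion, may withdraw a subject from this study based upon his/her professional judgment". No qualifying reasons, time limit or independent review are attached. For a withdrawn patient a Lost to Follow-up "case report form should be completed detailing the reason for the patient withdrawal", the ethics committee is notified if applicable, and a patient withdrawn by the investigator is told by letter or according to the local committee. On care afterwards: "Subject withdrawn from the study will obtain standard medical treatment as foreseen at the investigational site". Replacement is restricted: "Subjects will not be replaced, unless they do not have surgery or intraoperatively it has been recognized the patient is not eligible" for the nail.

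Section 7.3 says: "Subjects who have been lost to follow-up and/or are missing CT data at 3 weeks will not be included in the primary study analysis". Section 7.4 defines the primary set only by whether the scan exists: "The primary analysis will be performed on the set of patients with non-missing CT data at 3 weeks (Full Analysis Set (FAS". It adds that "Sensitivity analyses will be presented for the intention-to-treat (ITT) patient group". Section 7.3 commits to missing-data sensitivity analyses but leaves the named methods (best case, worst case, tipping point) optional.

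Randomisation is preoperative (Sections 2.4 and 2.6). The arms differ by one added screw placed at surgery (Section 2.1). A CT is taken within 3 days of surgery and again at 3 weeks (Section 2.6). No masking of investigator or surgeon is described. Section 2.5 says only that personal information is deleted from the images before central review.

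**The concern.** Discretionary withdrawal normally lets a clinician stop a continuing study treatment. Here the treatment is complete when the wound is closed. A later investigator withdrawal stops no study treatment. What it can stop is the 3-week CT, study follow-up and adverse-event questioning at visits.

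The person deciding can know the arm and have seen the early post-operative images. Withdrawal may then depend on both arm and expected outcome, and the patients left in the primary analysis are no longer the groups that randomisation formed. Central CT reading cannot correct for scans it never receives. Section 8.1 gives the sponsor no source data, so the recorded reasons cannot be checked against source.

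The text also leaves the fate of a withdrawn patient open. Sections 7.3 and 7.4 disagree when the 3-week CT already exists. Investigator withdrawal is absent from the specific withdrawal criteria in Section 3.3 and from the lost-to-follow-up definition in Section 9, although Section 3.3 records it on the form of that name.

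**Working it through.** **1. The plan's own figure.** Section 7.1 uses 87.5% and 72.7%, two-sided 5%, 80% power and a Pearson test. With pooled variance and mean rate 0.801:

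n = [1.960·√(2·0.801·0.199) + 0.842·√(0.875·0.125 + 0.727·0.273)]² / 0.148² = (1.107 + 0.467)² / 0.0219 ≈ 113.

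The stated 113 per group is reproduced (114 if rounded up). The 5% attrition allowance is 0.05 × 120 = 6 patients per group.

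**2. What happens to an investigator-withdrawn patient.**

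| Situation | Section 7.3 | Section 7.4 |
|---|---|---|
| Withdrawn before the 3-week CT, no CT taken | Excluded | Excluded |
| Withdrawn after the 3-week CT | Excluded, if the Lost to Follow-up form defines the status | Included |

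Nothing requires the CT to be taken after an investigator withdrawal.

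**3. Size, under stated assumptions.** Take 120 per arm, true maintenance of 80% in both arms and withdrawals in the ASS arm only. Neither the 80% nor the withdrawal pattern comes from the documents. Expected ASS failures are 120 × 0.20 = 24. The bias is the change in the observed ASS maintenance rate:

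- 5 withdrawn at average risk (20%): 1 failure removed; 23/115 = 20.0% failures; bias 0.
- 5 withdrawn at twice average risk (40%): 2 failures removed; 22/115 = 19.1%; bias +0.9 points.
- 5 withdrawn at three times average risk (60%): 3 failures removed; 21/115 = 18.3%; bias +1.7 points.
- 20% of true failures withdrawn and no successes: 4.8 removed; 19.2/115.2 = 16.7%; bias +3.3 points.

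False positives favouring ASS were simulated with the planned test: z = (f_control − f_ASS) / √[f̄(1 − f̄)(1/n_ASS + 1/n_control)], where f is the observed failure proportion, counting z > 1.96.

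| Withdrawals, ASS arm only | False positives favouring ASS |
|---|---|
| None | 2.6% |
| 5 at twice average risk | 3.6% |
| 5 at three times average risk | 5.1% |
| 20% of true failures (about 4.8 patients) | 9.6% |

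At 72.7% maintenance the last row is 11.0%. As an extreme, if all 6 patients of the attrition allowance were ASS failures, the rate would be 10.8% at 72.7% and 14.9% at 80.1%. If the same selection operates in both arms, the rate stays at about 2.5%. Withdrawing control failures instead biases against ASS.

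**4. What the sensitivity analyses can show.** At about the planned rates with 6 missing per group, observed cases give 100/114 against 83/114, p = 0.005. Counting missing ASS patients as failures and missing controls as successes gives 100/120 against 89/120, p = 0.083. A sensitivity analysis can therefore expose the dependence on missing patients, but under Section 7.4 the primary result remains the first one.

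**The case against.** The clause is conventional, and four points against the concern have force.

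- **Timing.** The discretion also covers the interval between randomisation and surgery, when the allocated treatment can still be stopped. After surgery, withdrawal spares a patient further study scans and visits. A reader might infer that the clause serves no purpose except to delete outcomes. The documents do not support that.
- **Foresight.** The endpoint is maintenance of the immediate post-operative position, so a poor early position is not itself a failure. A surgeon can only guess who will re-displace. This is why the 9.6% figure, which assumes perfect prediction in one arm, is an upper bound for about five withdrawals and not an expectation.
- **Route to exclusion.** A patient who already has a 3-week CT stays in under Section 7.4. Exclusion of every withdrawn patient is not settled by the text.
- **Safeguards.** Reasons are recorded, replacement is restricted, the sponsor tracks follow-up (Section 11.3), and ITT and missing-data sensitivity analyses are planned.

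These points limit the size and the wording. They do not remove the concern: the safeguards make selective withdrawal visible, but none keeps the patient in the primary analysis. A recorded reason does not restrict the decision.

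**Conclusion.** The concern holds as an avoidable risk of bias and an inconsistency between Sections 3.3, 7.3, 7.4 and 9. It is not an arithmetic error, and the sample size is sound.

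Under the 80% scenario, about five selective ASS withdrawals move the false-positive rate favouring ASS from 2.6% to between 3.6% and 5.1%, with 9.6% if every withdrawal is a future failure. These figures rest on one-sided selection and an assumed number of withdrawals; the documents give neither a rate nor reasons. Five withdrawals is fewer than the 6 per group that the plan already accepts, so by number alone such a pattern would look like ordinary attrition.

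That the investigator knows the arm is an inference from the absence of any masking and from the nature of the procedure. A reader might go further and conclude that the Type I error rate in Section 7.4 is already lost, or that misuse is expected. The documents support neither: the inflation is conditional on behaviour they do not describe. Nor does the bias concern require a ban on all investigator withdrawal.

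**What to change.** - **Section 3.3:** state that after surgery an investigator's decision does not by itself end data collection. The reason is recorded and, unless the subject withdraws consent, the 3-week CT and adverse events are still collected where feasible. Keep the recorded reason and the notification letter, since both leave a trace.
- **Section 7.3:** replace the exclusion of lost-to-follow-up subjects with a rule that any 3-week CT obtained is read centrally and analysed in the randomised arm, and that investigator withdrawal is never a reason to leave it out. This also removes the conflict with Section 7.4.
- **Section 9:** say how investigator withdrawals are classified, so that the form and the lost-to-follow-up definition agree.
- **Study report:** give the number of investigator withdrawals by arm, with timing and reasons.

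The cost is protocol and SAP wording plus a little follow-up effort for withdrawn patients. There are no extra patients and no unscheduled scans. The sample size does not change: at the planned rates power is 80.3% with 114 per group and 82.3% if all 120 are retained.

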1.2 DEVICE / IMPLANT DESCRIPTION

The devices used in this study are as follows:

- ZNN CM Asia Nail
- ZNN CM Lag Screw
- ZNN CM locking screw
- ZNN CM Nail Cap

All implants are made from titan alloy. With ASS group, ACE 4.5/5mm Cannulated Cortical Lag Screw 20mm

Thread which made from titan alloy can be used.

Fig 2. ZNN CM Asia Nail with ASS

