9. DATA REPORTING

Within 6 months of the study close the sponsor will present a final study report to summarize all data collected throughout the study duration, complications throughout the course of the data collection, and general findings.

The report will contain the results of all primary and secondary endpoints. Also, patient follow-up will be analyzed throughout the data collection according to the following definition and equations:

- Lost To Follow-Up:
1. Death
 2. Implant Removal: Date of revision, all component part numbers removed, reason for revision, and any relation to study device.
 3. Revision of Components: date of revision, all component part numbers removed, and reason for revision Consent Rescinded

**Bearing revisions in which only the polyethylene is replaced will not be withdrawn from the study.*

Percentage Follow-up = # Patients with Follow-Up x 100
(Theoretically due – Lost To Follow-Up)

Percentage Accounted for = (# with Follow-Up + Lost To Follow-Up) x 100
Theoretically due

Both the sponsor and investigators will make reasonable efforts to publish the results of this trial.

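### Implant removal counts as study withdrawal (3.3) and, with component revision, as loss to follow-up (9), so re-operated patients have no further planned safety follow-up

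*Combined protocol and SAP*

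**What the plan says.** Section 3.3 gives three specific withdrawal criteria: written withdrawal of consent, death, and "Implant Removal: Date of revision, all component part numbers removed, and reason for revision". For any of them, "If patients meet any of the following criteria, a subject withdrawal form should be completed, and below data documented on the form". On what follows, it says only that "Subject withdrawn from the study will obtain standard medical treatment as foreseen at the investigational site". No later study visit or safety contact is described.

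Section 9 defines loss to follow-up for the final report. Its list includes "Implant Removal: Date of revision, all component part numbers removed, reason for revision, and any relation to study device" and also "Revision of Components: date of revision, all component part numbers removed, and reason for revision". The one exemption reads "Bearing revisions in which only the polyethylene is replaced will not be withdrawn from the study". The follow-up percentage divides patients with follow-up by those theoretically due minus those lost to follow-up.

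Section 5 asks for every adverse event to be recorded on its own form and has patients questioned about events at each later follow-up visit. Sections 2.4 and 2.6 plan two visits after the immediate postoperative one: 3 weeks, and an optional 16 weeks. Section 2.3 makes safety a secondary endpoint.

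Section 1.2 lists the nail, lag screw, locking screw and nail cap. It then adds, for one arm only, "With ASS group, ACE 4.5/5mm Cannulated Cortical Lag Screw 20mm".

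**The concern.** Having an implant removed is an outcome of treatment. It is not a decision to leave the study. Under these sections a patient who has been re-operated on, is alive and still consents is handled like one who has died or rescinded consent. Section 10 lists infection, nerve damage, bone fracture and loss of fixation among the expected risks, and re-operated patients are a group in whom further events of this kind matter. Planned questioning stops for exactly these patients.

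Three further problems come from the same text:

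- Sections 3.3 and 9 do not agree on whether component revision ends participation.
- The only exemption concerns a part that this nail system does not have.
- Neither implant nor component is defined, so sites may differ on whether removing the ASS screw alone is a withdrawal. That question can arise only in the ASS arm.

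**Working it through.** The plan states no figure on this point to reproduce, and it gives no removal or revision rate. The check sets the sections side by side and then works through the section 9 formula.

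**1. Which events end participation**

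| Event | Section 3.3 | Section 9 |
|---|---|---|
| Implant removal | withdrawal criterion | lost to follow-up |
| Component revision | not listed | lost to follow-up |
| Polyethylene-only bearing revision | not mentioned | exempt from withdrawal |
| ASS screw removed, nail left in place | not addressed | not addressed |

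The section 1.2 devices include no bearing, so the exemption can never apply. Its wording nevertheless implies that other component revisions do lead to withdrawal, which 3.3 does not say.

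**2. What follow-up is lost**

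- Removal before the 3-week visit: the 3-week visit and the optional 16-week visit.
- Removal after the 3-week visit: the optional 16-week visit only.

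Section 5 ties questioning about adverse events to these visits, and no section provides another route for a withdrawn patient.

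**3. Effect on the reported follow-up percentage**

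Formula (section 9): percentage follow-up = 100 × patients with follow-up / (theoretically due − lost to follow-up).

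Take one arm of 120 (section 2.1). Assume *k* removals, with no other losses and no deaths, so that the effect of removals stands alone. Then 120 − *k* patients are followed. The formula gives 100 × (120 − *k*)/(120 − *k*), while the share actually followed is 100 × (120 − *k*)/120.

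| Assumed removals *k* | Section 9 percentage | Actually followed |
|---|---|---|
| 1 | 119/119 = 100% | 119/120 = 99.2% |
| 3 | 117/117 = 100% | 117/120 = 97.5% |
| 6 | 114/114 = 100% | 114/120 = 95.0% |
| 12 | 108/108 = 100% | 108/120 = 90.0% |

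Section 9's second measure, percentage accounted for, adds the lost patients to the numerator: for *k* = 12, (108 + 12)/120 = 100%. Neither measure shows the gap. By contrast, 12 patients who simply missed the visit are not on the section 9 list and stay in the denominator, giving 108/120 = 90%.

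**4. Difference between arms**

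The ASS arm has one more removable part, which could make the rule act more often there. Against that, section 7.1 assumes loss of reduction in 100 − 72.7 = 27.3% of controls and 100 − 87.5 = 12.5% of ASS patients. If loss of reduction leads to revision, the rule could act more often in the control arm. The documents do not allow these two effects to be weighed.

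**The case against.** The strongest reply is that little is lost. The removal is recorded with date, parts and reason, and any adverse event goes on the section 5 form with its relation to the device and its outcome. Section 7.4 compares safety outcomes between arms. Section 5 sets no cut-off for adverse events at withdrawal, and the sentence on standard care describes treatment without forbidding further recording. After week 3, only one visit that is optional for everyone is at stake.

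Most of this is correct and limits the size of the point. It does not remove it. Recording the removal does not capture what happens afterwards, and no section provides for that. That safety collection ends at withdrawal is an inference, but a strong one, since questioning is tied to visits the patient no longer has. Section 7.4 also puts secondary analyses on patients with a 3-week CT and defines no separate safety set. Read literally, a removal before that CT could leave the safety comparison too.

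A reader might infer more than the text supports in three places:

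- **That removing the ASS screw alone triggers withdrawal.** It could, because nothing exempts it, but the terms are undefined and the case is not mentioned.
- **That the rule makes ASS look safer.** The direction is unknown, as step 4 shows, and a recorded screw removal would itself count against ASS.
- **That follow-up stops at a serious device event.** A removal need not be serious or device-related; section 9 itself asks for any relation to the device.

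**Conclusion.** The point holds in limited form. Sections 3.3, 5 and 9 together leave living, consenting, re-operated patients without planned safety questioning after the removal. For component revision the two lists conflict, so handling is uncertain. The loss per patient is at most the 3-week visit and the optional 16-week visit.

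The number of patients cannot be estimated from the documents, and the counts in the table are assumptions chosen to show how the formula behaves. What does not depend on them is that the section 9 percentage cannot register removals or revisions as missing follow-up: with these as the only losses it reads 100% whatever their number.

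An ASS-only trigger is possible but not stated, and no direction of bias between arms can be claimed. The flaw affects a secondary safety description and the follow-up reporting. It should be corrected, but it does not by itself threaten the trial's main conclusion. How removals before the 3-week CT are scored for the primary endpoint is a separate question under section 7.3.

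**What to change.** - **Section 3.3:** take implant removal off the list of withdrawal criteria. State that patients with any removal or revision remain in the scheduled study visits and adverse event collection unless they die or rescind consent. Keep the date, parts and reason, recorded as event data.
- **Section 9:** take implant removal and component revision out of the lost-to-follow-up definition and report both as outcomes by arm. State that the ASS screw counts as a component, so that all sites record its removal in the same way. Delete the polyethylene sentence.
- **Both sections:** use the same definitions of implant, component, removal and revision.

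The cost is a wording amendment and a few extra forms. The reported follow-up percentage may fall if re-operated patients are not seen. In the illustration with 12 removals, it would be 108/120 = 90% if none of them attended and 120/120 = 100% if all did, and either figure would then be a true one.
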